Study Design: To address Aims 2 and 3, we will use a randomized controlled trial. A total of 300 adults with arthritis, aged 18 and older, will be recruited throughout the community. Participants will be randomized to either Walk with Ease (WWE-T) or Wait list control. The WWE-T program will be 6 weeks in duration, like the AAEBI version of WWE, and will include two phone calls each week: one group call and one individual call. Assessments will be conducted before randomization, immediately after the 6-week program, and at 6 months and 1 year. There will be no intervention-specific contact with participants following the 6-week program. Primary outcomes are pain and physical function. Secondary outcomes are weight, objectively measured physical activity, depressive symptoms, self-efficacy, weight, blood pressure, work loss, and health care utilization.

Procedures:

Recruitment: Participants will be recruited using effective recruitment strategies used in the past as well as with the assistance of DHEC, the SC Department of Aging, and Lupus Foundation of America. All recruitment procedures are provided in more detail in section D.2.

Screening: Participants will be screened by telephone or online to ensure they meet study criteria. Interested and eligible participants will be scheduled for a baseline appointment and mailed an informed consent form and study materials to review prior to their baseline visit.

Informed Consent: At the baseline appointment, study staff will review the consent form with participants and answer any questions participants may have regarding their participation. To ensure the consent form is understandable to the study population, the consent form will be written using short sentences and non-technical terms, with a reading level at or below an eighth-grade level. Interested participants will sign the approved informed consent document and will be given a copy for their records.

Randomization: After completing the baseline assessment, participants will be randomized in a 1:1 ratio to either: (1) WWE-T or (2) Wait list control. Randomization, stratified by age (<65 years and ≥65 years) and sex, will be done using randomly permuted blocks. The study team member conducting the randomization phone call will open the sealed envelope and reveal randomization to the participant. The study team member will describe the condition, provide the appropriate program materials via mail, and review study expectations.

Randomized Conditions:

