- 1.) **Walk with Ease by Telephone Program.** Our Walk with Ease by Telephone (WWE-T) program is adapted from the original 6-week community-based group walking program developed by the Arthritis Foundation for adults with arthritis. After randomization, all participants in WWE-T will be given an Arthritis Foundation Walk with Ease Guidebook and a brief overview of the program. The program uses motivational strategies, which includes action planning, goal setting, and social support. Additionally, WWE provides participants with appropriate health education necessary to safely increase walking and exercise into their daily lives and assists in tailoring the program to fit individuals' unique needs and goals. Examples of topics include exercise and arthritis, preparing to walk (e.g., identifying appropriate footwear, location, and walking pace), stretching, and overcoming barriers including pain and discomfort. Participants will work towards walking at least 30 minutes/day for 3 days/week, as this goal is consistent with the evidence-based WWE program.

Phone Sessions for WWE-T. Participants in WWE-T will receive 2 phone calls each week for 6 weeks. Each week, one phone call will be one-on-one with a WWE certified trained leader and the second call will be a group call led by the WWE leader and will include other WWE-T participants. During group phone sessions, the WWE-T leader will cover topics described above relating to exercise and arthritis. Group calls will include 12-16 participants, as recommended by previous studies. Group calls will last approximately 45 - 60 minutes in duration. During

University of South Carolina Protocol v4

individual phone sessions, the WWE leader will focus on tailoring the WWE-T program for the individual and setting weekly walking goals. The WWE leader will also ensure that safety issues are assessed and addressed. Individual calls will be approximately 10 – 15 minutes in duration. WWE leaders will document attendance, topics discussed, any participant symptoms/adverse events, and call durations.

- 2.) **Wait List Control.** Participants randomized to Wait List Control will receive the WWE-T program following the completion of the 1-year assessment. Besides scheduling for and sending reminders for each assessment, there will not be contact with participants in the Wait List Control.

Measures:

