Data Analysis: After data collection and cleaning, baseline characteristics of the groups will be compared. Variables which differ between the groups at baseline will be used as covariates in the outcome models. For each of the Aim 2 primary and secondary outcomes, a generalized linear model will estimate group means at baseline, six weeks, six months and one year. Each model will include factors for group (2 levels), time (4 levels), group-by-time interactions and the required covariates. In the event of participants being lost to follow-up or otherwise missing data from the 6-week, 6-month and/or 1-year times, the models will provide estimates using Full Information Maximum Likelihood with robust standard errors, interpretable under an Intent to Treat principle.

For each outcome at each follow-up time, a statistically significant (at the 0.05 level) group by time interaction in the hypothesized direction will be interpreted as supporting the research hypothesis. The magnitude of each intervention effect will be computed by a pre-defined contrast of baseline to follow-up change in the group minus baseline to follow-up change in the Wait List Control, adjusted for covariates. All four time points for each outcome will be examined with a single model to best account for the full covariance structure over time. All analyses will be completed using SAS (SAS Institute Inc, Cary, NC).

We will evaluate the recruitment and retention strategies used during the proposed study, focusing on successful strategies used to increase participation of adults with arthritis, particularly among those with low socioeconomic status. During the recruitment and screening of participants, participants will be asked to report how they heard of the program. We will also examine recruitment numbers over time in relation to recruitment activities. Following the completion of the program, we will categorize recruitment avenues (e.g., saw flyer, word of mouth) and sites (e.g., local rheumatologist site, lupus support group) and calculate the percentage of those screened, not interested, ineligible, and enrolled. Percentages will be calculated among the total sample recruited as well as specifically for those of low

University of South Carolina Protocol v4

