Exclusion Criteria: Participants will only be excluded if they have any contraindications to exercise (besides arthritis) per the Physical Activity Readiness Questionnaires,⁵⁶ are pregnant, breastfeeding, or planning to become pregnant in the next year, have a serious cognitive impairment, or are currently or have previously participated in a WWE program within the last 12 months.

Sample Size: In order to assure sufficient statistical power to detect clinically meaningful effects, we relied on information from a previous study by Wilcox, et. al.¹¹ for an estimate of variability in the VAS Pain scale and physical function tests including the 30-second chair stands and six-minute test. The Steps to Health study evaluated two 12-week self-directed multicomponent exercise programs for adults with arthritis.¹¹ Clinically meaningful magnitude of changes were suggested by Bennell et al.⁵⁷ as 11 points for VAS pain, 1.3 repetitions for the chair stand test and 20-50 meters for the six-minute walk. Estimated power is based on a simplified analysis (t-tests) without covariate adjustments. A statistical significance level of 0.05 was used.

A sample of 120 participants per group would provide 80% or greater power to detect a clinically meaningful difference in each primary outcome, with a minimum effect size of $d=.37$, assuming that the variability within our sample is comparable to that observed in the earlier study from a similar population (see Table 2). We anticipate that some participants may be lost to follow-up before the conclusion of the study. Therefore, we propose inflating the required sample size by 25% to account for potential attrition and recruiting 300 participants total, with 150 to be randomized into each treatment condition.

2.RECRUITMENT PLANS:

Participants will be recruited using effective recruitment strategies used in the past as well as with the assistance of DHEC, the SC Department of Aging, and Lupus Foundation of America across Richland,

University of South Carolina Protocol v4

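### WWE-T is delivered in call groups of 12-16 against an ungrouped wait list, but neither the Aim 2 models nor the power calculation allows for correlation within call group

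*Combined protocol and SAP*

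**What the plan says.** Randomization is individual (section C, Randomization): "participants will be randomized in a 1:1 ratio to either: (1) WWE-T or (2) Wait list control". In WWE-T, each week has one individual call and one group call (section C, Phone Sessions for WWE-T): "the second call will be a group call led by the WWE leader and will include other WWE-T participants". On size: "Group calls will include 12-16 participants, as recommended by previous studies". For the comparator, apart from scheduling and reminders, "there will not be contact with participants in the Wait List Control" until the program is offered after the 1-year assessment.

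The Data Analysis section lists the model terms: "Each model will include factors for group (2 levels), time (4 levels), group-by-time interactions and the required covariates". It handles missing data by full-information likelihood with robust standard errors, names no clustering unit for those errors, and speaks of covariance only over time.

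The Sample Size text (section D.1) describes its method thus: "Estimated power is based on a simplified analysis (t-tests) without covariate adjustments". On the test level it adds: "A statistical significance level of 0.05 was used". Its conclusion reads: "A sample of 120 participants per group would provide 80% or greater power to detect a clinically meaningful difference in each primary outcome". The smallest d it covers is 0.37. Call group, leader, ICC and design effect are not mentioned in the analysis or the sample-size text.

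**The concern.** This is a partially nested design: people are randomized one by one, then one arm is treated in groups and the other is not. Members of a call group share a leader and each other's company. The documents give reasons to expect some similarity in outcome. Social support is a listed program strategy, and its possible absence is the stated weakness of the self-directed format. Group calls last 45-60 minutes and individual calls 10-15, so group time is between 45/(45+15) = 75% and 60/(60+10) = 86% of weekly contact.

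If members' outcomes are positively correlated, the WWE-T mean varies more than independent data would suggest. The planned model does not see that extra variance. Its standard errors are then too small, its tests reject too often, and the stated power is not what a valid analysis delivers.

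**Working it through.** **Inputs.** From the documents: 120 analysed and 150 randomized per arm, d = 0.37, alpha 0.05, call groups of 12-16. Sidedness is not stated; two-sided reproduces the plan's figure. Assumed, because the documents do not give it: ICC 0.01-0.05, with 0.10 shown as an upper case. The table of standard deviations is not in the text available, so SD = 1 and d is used directly.

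**1. The plan's own figure.** Under independence SE = sqrt(2/120) = 0.1291 and 0.37/0.1291 = 2.866. Power = Phi(2.866 - 1.960) = 81.8% (81.4% by noncentral t). The stated 80% or greater is reproduced. Recruitment is 120 x 1.25 = 150 per arm, 300 in all.

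**2. Number and size of groups.** 150/16 = 9.4 and 150/12 = 12.5, so about 9-13 groups. At the midpoint, 150/14 is about 11 groups. The plan's inflation leaves 120/150 = 80% analysed, so m = 14 x 0.8 = 11.2 members per group.

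**3. Formulas, with clustering in one arm only.**
- Design effect in WWE-T: DE = 1 + (m - 1) x ICC
- Correct SE over unadjusted SE: R = sqrt((DE + 1)/2)
- Two-sided type I error of the unadjusted test: 2 x (1 - Phi(1.96/R))
- Power, design effect alone: Phi(0.37/sqrt((DE + 1)/120) - 1.96)

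Example at ICC 0.05: DE = 1 + 10.2 x 0.05 = 1.51; R = sqrt(2.51/2) = 1.120; type I error = 2 x (1 - Phi(1.75)) = 8.0%. SE = sqrt(2.51/120) = 0.1446, 0.37/0.1446 = 2.558, and power = Phi(0.598) = 72.5%.

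**4. Results.** The simulated columns use 120 per arm and 11 WWE-T groups. Small-sample power is from a Welch test on call-group means; its ICC 0 entry is the matching Satterthwaite approximation.

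| ICC | DE | R | Type I, formula | Type I, simulated | Power, DE alone | Power, small-sample df |
|---|---|---|---|---|---|---|
| 0 | 1.00 | 1.000 | 5.0% | - | 81.8% | 79.6% |
| 0.01 | 1.10 | 1.025 | 5.6% | 5.6% | 79.8% | 78% |
| 0.02 | 1.20 | 1.050 | 6.2% | 6.1% | 77.9% | 76% |
| 0.05 | 1.51 | 1.120 | 8.0% | 8.2% | 72.5% | 70% |
| 0.10 | 2.02 | 1.229 | 11.1% | 10.6% | 64.5% | 61% |

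At ICC 0.05, true coverage of a nominal 95% interval is about 100 - 8.2 = 91.8%. By the design effect alone, power at d = 0.37 drops below 80% once the ICC exceeds about 0.009.

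**5. Separating the two losses.** At ICC 0.05 the design effect costs 81.8 - 72.5 = 9.3 points. Basing the degrees of freedom on about 11 groups costs a further 2-3 points, and about 2 points even at ICC 0.

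**6. Decision rule.** The plan counts a result as support only if it lies in the predicted direction. With a two-sided test, false support is half the two-sided rate: 5.6/2 = 2.8% to 8.2/2 = 4.1% for ICC 0.01-0.05, against a nominal 2.5%.

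**The case against.** **The ICC is unknown.** A reader might infer that the intervals are too narrow and that power is below 80% as matters of fact. The documents do not support that: both need a positive ICC, and none is given. At 0.01 the harm is small. The direction is certain for any positive value; the size is an assumption.

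**Group structure is partly inferred.** A reader might assume that the same 12-16 people stay together for six weeks, or that groups were formed to create social support. Fixed membership is likely but not stated, and the group size is justified only by earlier studies. The number of leaders is also not given; if a few leaders run several groups each, clusters are larger and the loss could be greater.

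**Robust standard errors.** One might argue that these already cover the problem, or conversely assert that they are clustered on the participant. The text names no unit, so neither reading is established. They would help only if clustered on call group, and with about 9-13 groups would then need a small-sample correction.

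**Not every contrast need be equally affected.** Intervention contact ends at week 6, so call-group correlation may be weaker at 6 months and 1 year. It may also be weaker for outcomes such as blood pressure or health-care use.

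**Power has reserves.** The plan itself calls its t-test basis simplified. If d is scaled to a score SD, the planned change-from-baseline contrast can gain precision. With baseline correlation rho (assumed), the variance is [4(1 - rho) + (m - 1) x ICC]/120. At ICC 0.05 and m = 11.2, power is 73%, 80% and 87% for rho of 0.5, 0.6 and 0.7. If d is scaled to a change SD, there is no such gain. A primary outcome with d = 0.45 would have about 88% power at ICC 0.05 without it. This stands as a reason not to assert that power is below 80%. It does not repair type I error or coverage.

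**Conclusion.** The omission is documented: neither the Aim 2 models nor the sample size allows for call-group or leader correlation. The consequence is conditional. If the ICC is positive, WWE-T versus control intervals will be too narrow.

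For assumed ICCs of 0.01-0.05, two-sided type I error is about 5.6-8.2%, and false support for the hypothesis is roughly 3-4% against 2.5%. Power at the minimum effect size is about 80-73% from clustering and 78-70% with appropriate degrees of freedom, against 81% under independence. These figures rest on 120 analysed per arm, 11 groups with stable membership, and no covariate or baseline gain. They apply best at 6 weeks and may overstate the effect later. Outcomes with a larger d have more reserve.

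A reader might conclude that the trial must enrol more people. That does not follow: valid inference needs a different error structure, not a larger sample. Equally, the analysis change does not bring power back to 80%, which is why the stated power should be qualified.

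**What to change.** 1. Record call-group ID and leader ID for every WWE-T participant. Leaders already log attendance, so this adds little work.
2. Before outcomes are seen, specify a partially nested model for the Aim 2 outcomes: the planned fixed effects and within-person covariance, plus a random call-group effect acting only in the WWE-T arm and only at follow-up, with each control as a singleton. Say how leader will be considered.
3. Fit it by REML with Satterthwaite or Kenward-Roger degrees of freedom, replacing the unspecified robust errors. This remains likelihood-based, so the planned approach to missing follow-up is kept.
4. State in advance what happens if the call-group variance is estimated at zero, since about 9-13 groups estimate a small component poorly.
5. Replace the unqualified 80% with power or detectable d over an ICC range such as 0.01-0.05. By the design effect alone at m = 11.2, d detectable with 80% power is (1.960 + 0.842) x sqrt((DE + 1)/120): 0.362 under independence, 0.371 at ICC 0.01 and 0.405 at ICC 0.05.

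The cost is SAP wording, two ID variables and a modest addition to the SAS code. Intervals will be slightly wider and the stated power less favourable.

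### Covariates are chosen by baseline differences between randomized groups, and as modelled they cancel from the change contrast, so the effect called adjusted is essentially unadjusted.

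*Combined protocol and SAP*

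**What the plan says.** The covariate rule is in section C, Data Analysis. It begins with timing: "After data collection and cleaning, baseline characteristics of the groups will be compared". It continues: "Variables which differ between the groups at baseline will be used as covariates in the outcome models". No test, threshold or list of candidate variables is given.

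The model terms follow: "Each model will include factors for group (2 levels), time (4 levels), group-by-time interactions and the required covariates". Baseline is one of the four time levels, so it is a response. No covariate-by-time terms are listed, and adjustment for an outcome's own baseline value is not mentioned.

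The effect is a difference between arms in change: "The magnitude of each intervention effect will be computed by a pre-defined contrast of baseline to follow-up change in the group". The control arm's change is subtracted from this, and the plan labels the result as covariate-adjusted ("baseline to follow-up change in the Wait List Control, adjusted for covariates"). Missing follow-up is handled by "Full Information Maximum Likelihood with robust standard errors".

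Section C, Randomization, states that allocation is "stratified by age (<65 years and ≥65 years) and sex", in permuted blocks. Neither factor is named as a model term in Data Analysis.

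**The concern.** Baseline differences between randomized groups are due to chance. Whether a variable happens to differ says nothing about whether it predicts the outcome, which is the reason to adjust. Three things follow.

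- The adjustment set is unknown until all outcome data are in, although the contrast itself is called pre-defined.
- The two factors that shaped the randomization are the ones least likely to meet the rule, because stratified blocks balance them.
- Because covariates enter without time interactions, they drop out of a change-from-baseline contrast. The rule can flag an imbalance and the report can describe the effect as adjusted while the estimate has not moved.

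At stake, for every Aim 2 outcome, are an error left in the estimate in the trials where the rule is triggered by a variable that predicts change, and the precision that baseline adjustment would give.

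**Working it through.** **1. The plan's own figure.** Section D.1, Sample Size, gives 120 per group, d = 0.37, level 0.05 (two-sided assumed) and t-tests without covariates. Power = Φ(0.37 × √(120/2) − 1.960) = Φ(2.866 − 1.960) = Φ(0.906) = 81.8%; the noncentral t gives 81.4%. Inflation: 240 × 1.25 = 300. The stated 80% or more and N = 300 reproduce. No covariates enter this calculation, so a change in the covariate rule does not change N.

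**2. Can the rule select the strata?** Assume that *differ* means p < 0.05, with half the sample aged 65 or over and 75% of one sex. In simulated stratified permuted blocks with N = 300, age group met p < 0.05 in 0 of 3000 trials, and so did sex, for blocks of 4 and again for blocks of 8. An unrelated, unstratified variable was selected about 5% of the time. If 10 to 20 independent variables are screened, the chance that at least one enters is 1 − 0.95^10 = 40% to 1 − 0.95^20 = 64%.

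**3. Does a main-effect covariate change the contrast?** With an identity link, the adjusted mean of group g at time t is ȳ(g,t) − c·(x̄(g) − x̄), where c is the covariate's coefficient. The second term does not depend on t. Change within a group is therefore ȳ(g,t) − ȳ(g,0) whatever c is, and the difference in change is the unadjusted one. The same algebra covers an outcome's own baseline entered as x.

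Maximum-likelihood fits with four times, unstructured covariance, 150 data sets of N = 300 and an assumed residual correlation of 0.6 agree:
- Complete data: largest shift in the 1-year contrast 6e-14; SE 0.102 with and without covariates.
- About one third lost by 1 year (assumed): mean estimate 0.361 to 0.363, SE 0.1178 to 0.1173, largest shift in any data set 0.035 SD.

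**4. What stays in the estimate?** With 150 per group, a just-significant baseline imbalance is 1.96 × √(2/150) = 0.226 SD. If the outcome has equal variance at both visits and correlation r, an imbalance D carries r·D into follow-up, so the change contrast is off by (1 − r)·D in size:

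| assumed r | error (SD) | share of d = 0.37 |
|---|---|---|
| 0.7 | 0.3 × 0.226 = 0.07 | 18% |
| 0.5 | 0.5 × 0.226 = 0.11 | 31% |
| 0.3 | 0.7 × 0.226 = 0.16 | 43% |

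The last column assumes that 0.37 is in single-visit SDs. In simulated null trials at r = 0.5, kept only when the baseline imbalance was significant, the change contrast was off by 0.134 SD on average and the baseline-adjusted analysis by 0.000.

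**5. Where is the precision?** Complete-data SE of the 1-year contrast, from the fits in step 3:
- as written: 0.102
- age, sex and a prognostic covariate, each with time interactions (no true interaction): 0.102
- common baseline mean only: 0.094
- common baseline mean plus those covariates and interactions: 0.091

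With dropout, the first and last become 0.118 and 0.107. The empirical SDs there were 0.115 and 0.112, and an SD from 150 runs carries a Monte Carlo error of about 1/√300 = 6%, so the gain under dropout is less certain.

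By formula, at 120 per group with d in single-visit SDs, the SD is √(2(1 − r)) for plain change and √(1 − r²) after baseline adjustment. Power is 68% against 85% at r = 0.3, 82% against 91% at r = 0.5, and 96% against 98% at r = 0.7.

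**The case against.** The best defence has several parts, and much of it stands.

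- *Late selection.* A reader might infer that picking covariates after data collection opens the door to result-driven modelling. Under the model as written it hardly can, because covariates that cancel cannot steer the contrast. Selection also uses baseline data only, under a rule stated in advance; the latitude lies in the undefined word *differ*. The risk becomes real only if time interactions or a non-identity link are used.
- *All imbalance stays in.* This goes too far. A covariate with the same effect at every visit is removed by differencing. With an imbalance of 0.24 SD and a constant effect of 0.5, the simulated bias was 0.001; when the effect grew from 0.5 to 0.7 it was 0.049, matching 0.24 × 0.2 = 0.048. Only variables that predict change matter.
- *Strata excluded.* The text neither names nor forbids age and sex. Their absence is an inference from the only entry rule given.
- *Precision lost from the strata.* Not shown. If age and sex explained 2% or 5% of the variance in change (assumed), the SE would fall by only about 1.0% or 2.5%.
- *Exact cancellation.* It needs an identity link and complete data. The plan allows generalized linear models and expects attrition.
- *How often chance covariates enter.* This depends on an assumed p < 0.05 screen of independent variables. The plan states neither, and several scores overlap.

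What the defence does not answer is the mismatch itself. The plan reports an effect as adjusted when its stated terms leave it all but unchanged, and it makes no provision for the one baseline variable that matters most.

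**Conclusion.** The concern holds, as a should-fix. The rule reacts to chance differences, gives the stratification factors no practical way in, and yields a contrast that is essentially unadjusted. When an outcome's own baseline is just significantly imbalanced, the error left in the estimate is 0.07 to 0.16 SD for r from 0.7 to 0.3. These correlations, equal variances, and the reading of *differ* as p < 0.05 are assumptions; the documents give none of them.

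This error is conditional on the imbalance. A reader might infer that the planned estimator is biased overall, or that the trial is underpowered. Neither follows: over all randomizations the difference in change is centred on the true effect, and the stated power and N reproduce. What is lost is protection in the trials where the rule is triggered, and precision. The precision comes mainly from baseline-outcome adjustment (SE 0.102 to 0.094 alone, 0.091 with covariates, at an assumed residual correlation of 0.6).

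**What to change.** In section C, Data Analysis:

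1. Delete the rule that selects covariates by baseline comparison. Keep the baseline table as description, with no tests that feed the model.
2. Name the covariates for every Aim 2 model: age stratum (<65, ≥65) and sex, each with its interaction with time.
3. Adjust for the outcome's own baseline value, in one of two stated ways: a common baseline mean for both groups in the four-time-point model, or baseline as a covariate with only the three follow-up times as responses. The first keeps every randomized participant with a baseline value in the likelihood. Restate the effect contrast to match.
4. Allow any further covariate only if it is named, with how it enters the model, before anyone analysing the data has seen outcomes by randomized group. The plan masks only assessment staff, so this point in time has to be written down.

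The cost is wording and a few degrees of freedom: two binary factors at four times use 8 parameters per model, out of about 300 participants. All the variables are already collected, and the inclusion criteria require baseline measures to be completed. The planned N does not change.
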